3.2 Primary and secondary endpoints

Primary endpoint

Maximal isometric force of the back extensor

The maximum voluntary isometric contraction (in Newtons) of the back extensor is measured with the CE-certified ILEX machine Myosom (Heftec GmbH, Oberurnen, Switzerland) before, after 6 sessions and after 12 sessions of resistance training and diathermy therapy to examine strength growth. ILEX resistance machines are designed to primarily train the lumbar muscles by stabilizing the pelvis through specially designed restraints (Steele et al., 2015b). Participants are seated in the machine in a semi-sitting position with the feet placed on a footrest and the thoracal back leaned against a squared restrained. The movement arm is locked causing a slight flexion in the lumbar back and restrain belts are secured around the pelvis and shoulders. The participants are advised to extend their back slowly and continuously against the upper-back pad for 2 to 3 seconds. Peak torque is registered electronically.

Secondary endpoints

Isometric back extension strength endurance

Isometric back extension endurance (in seconds) is assessed using the Biering-Sørensen test before, after 6 sessions and after 12 sessions of resistance training and diathermy therapy to confirm the strength growth in the back extensor. The Biering-Sørensen test is the most widely used test in published studies evaluating the isometric endurance of trunk extensor muscles. It is a rapid, simple, and reproducible test (Demoulin et al., 2006). The participant is lying prone on an examination table with the upper border of the iliac crests in line with the edge of the table. The lower body is secured to the table by three straps around the pelvis, knees, and ankles. With the arms folded across the chest, the participant is asked to hold the upper body isometrically in a horizontal position. It is measured how many seconds the participant can keep the unsupported upper body touching a horizontal object (Biering-Sørensen, 1984).

Thickness of M. erector spinae

The thickness of the M. erector spinae (in millimeter) is measured using the ultrasound system Mylab2 (Esaote, Maastricht, Netherlands) in B-mode and the software Horos™ (Horos Project,

Annapolis, MD, USA) before, after 6 sessions and 12 sessions of resistance training to confirm the strength growth in the back extensor. Muscle strength is associated with the cross-sectional area of the muscles (Jones et al., 2008) and measuring the thickness of the M. erectors spinae with ultrasound has been shown to be a safe and easy method for estimating back muscle strength (Fujiwara et al., 2017). The participant is lying prone on the examination table. The probe head is coated with coupling gel and applied perpendicular to the muscle on the right side without pressure to not compress the dermal surface. The thickness of the longissimus is defined as the distance between the midpoints of fascia posterior and the outermost point of transversus process of the L3 vertebra (Fujiwara et al., 2017).

Lumbar flexibility

There is evidence that strength training is effective in improving the ROM (Afonso et al., 2021). Moreover, a diminished ROM is associated with muscle weakness. The lumbar flexibility is assessed with the help of a goniometer built into the ILEX machine and the sit-and-reach test before, after 6 sessions and 12 sessions of resistance training to control its association with the muscle strength growth. Participants are seated in the ILEX machine in a semi-sitting position with the feet placed on a footrest and the thoracal back leaned against a squared restrained. Restrain belts are secured around the pelvis and shoulders. The movement arm is deblocked and the participants are advised to move dynamically backwards and forwards as far as possible. Three repetitions are done, and peak flexion and extension are registered electronically. Additionally, the combined flexibility of the M. erector spinae and hamstrings is measured using the sit-and-reach test. The sit-and-reach test is probably the most widely used lineal measure of flexibility and it is a simple, easy to administer test with requiring minimal skills. The participant is seated in front of the test box, keeping the knees fully extended and the feet dorsiflexed against the foot-support. The participant is moving actively, slowly forward, bringing the body to the pain-free limit. The participant's hands move the block along the scale until the movement is terminated because the participant can go no farther. The final position is held with an isometric contraction for 2 seconds, and the distance is read on the scale. The test is repeated twice and an average score is taken for further analysis (Holt et al., 1999).

Skin temperature

Radiofrequency-based therapy at 448kHz in the capacity mode increases skin temperature by around 3°C (Kumaran & Watson, 2015). Skin temperature in the area of the M. erector spinae is measured twice, immediately after the first and last diathermy therapy, using infrared thermal imaging (FLIR A615 series, Emitec Industrial, Rotkreuz, Switzerland) and data analysis software (FLIR ResearchIR Max). Participants are placed on an examination table to receive the diathermy treatment. The camera is installed on top of the examination table to take a picture of the right side of the erector spinae immediately after the treatment without the participant moving.

Rating of perceived effort (RPE-E)

Training to momentary failure (MF) is considered to be optimal for improving strength. In submaximal efforts, the dose-response relationship for adaptations is not fully clear yet (Steele et al., 2016). The rating of perceived effort (RPE-E) provides a valid and easily accessible measure of exercise intensity in resistance training (Lea et al., 2022). We use the Borg's Category-Ratio-Scale (CR-10) for strength training (Buckley & Borg, 2011) which is based on the original 15-grade Borg's scale for ratings of perceived exertion (Borg, 1982). Immediately after completion of every single of the 12 training sessions on the back extensor machine, the examiner asks the participant "How hard do you think you're working?". The participant reports her/his perceived effort verbally with a number from 0 (no exertion at all) to 10 (maximal effort) orientating on a scale visually.

Rating of perceived discomfort (RPE-D)

Particularly in resistance training it is important to differentiate between the perception of effort (RPE-E) and discomfort (RPE-D) (Steele et al., 2016). Discomfort is the physiological and

unpleasant sensations associated with exercise. Increasing number of repetitions and longer time under muscular tension leads to higher discomfort. Therefore, higher discomfort is experienced in low load than in high load training (Fisher et al., 2018). We use a Category-Ratio-Scale (CR-10) for the RPE-D (Steele et al., 2016). Immediately after the completion of each of the 12 training sessions on the ILEX machine, the participant is asked to report her/his perceived discomfort verbally with a number from 0 (no discomfort) to 10 (maximal discomfort) orientating on a scale visually.

Rating of thermal sensation

Immediately after each of the 12 diathermy treatments, the participant is asked to rate the thermal sensation in the area of the back extensor according to the ISO 10551. The participant rates thermal sensation ("How does this feel like?") using a 9-point Likert scale from 4 (very hot) to -4 (very cold) (Fabbri, 2015).

Rating of perceived comfort

After completion of the rating of thermal sensation, participants are asked to rate the comfort felt during the diathermy treatment on a 5-point scale ranging from 0 "angenehm" to 4 "äusserst unangenehm" (1 "etwas unangenehm", 2 "unangenehm", 3 "sehr unangenehm") (Zhang et al., 2004).

3.3 Study design

This is a monocentric clinical trial with minimal risks and burden of the risk class A (KlinV, Art. 20). A block randomization with covariates (i.e. sex) is used. The preheating is done as a single blinded randomized controlled trial (RCT) with the sham group receiving a 10-minute diathermy treatment with the Tecar device turned off and not sending radiofrequency before each exercise session. The intervention group undergoes a 10-minute treatment with the Tecar device to induce 448kHz capacitive monopolar radiofrequency and facilitate warming up of deep tissues. In order to be able to carry out a single-blind situation as far as possible, the test subjects are not told that the therapy causes heat of the deep tissue and that this is the factor being investigated. Instead, we speak of high-frequency Tecar therapy and its known use to promote tissue healing processes.

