appendix 1.

12 sessions of back extensor resistance training on the ILEX machine take place over a 6-week period (twice a week). Before each exercise, a diathermy treatment is taking place. Before, after 6 sessions and after completion of the 12 sessions, tests are conducted on separate days.

On intervention days, the participants enter the RES laboratory in Landquart wearing sports clothing. First, they lay on an examination table in a prone position receiving a treatment with the diathermy device for 10 minutes from a trained examiner. The intervention group is treated with the diathermy device inducing 448kHz capacitive monopolar radiofrequency, warming up the deep tissues. The sham group receives a massage with the diathermy device without radiofrequency. Directly after the first and last diathermy treatment, a picture will be taken with an infrared camera (FLIR A600 series, Emitec Industrial, Rotkreuz, Switzerland). Then, participants translocate to the ILEX machine and are seated according to their individual settings. The training session lasts 12 minutes. Participants begin the training session with a dynamic warm-up of the lumbar extensor for 120s, followed by three sets of resistance training lasting 120s, 120s, and 150s respectively, and concluding with a final set of dynamic recovery lasting 60s. Between each set, a 30-second recovery is provided. Repetitions will be executed by taking three seconds from complete flexion to complete extension, ensuring standardization at 20 repetitions per minute. A metronome with 40 beats per minute will provide audible feedback. The ILEX machine emits an audible signal upon completion of each phase of the repetition to guarantee a complete ROM is achieved. A low load is used for the warm-up and recovery. For the three training sets, the initial load is based on the maximal isometric force and subsequently increased until volitional fatigue. Immediately subsequent to each training session, participants will be requested to provide their effort (RPE-E) and discomfort (RPE-D) values. Immediately after the first and final diathermy treatment before dislocating to the ILEX machine, participants skin temperature is measured while laying prone on the examination table making an imaging with the FLIR camera.

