On the examination days (BL, F/U1 and F/U2), the participants enter the RES laboratory in Landquart wearing sports clothing. At baseline, participants are asked to sign an informed consent form and are screened for inclusion and exclusion criteria. Participants are then asked for their age and sex, height is measured using a stadiometer (GPM Stadiometer, Zurich, Switzerland), and weight and lower body fat percentage are measured using a scale (TANITA-TBF 611 scale, Tokyo, Japan). At all three measurements (BL, F/U1 and F/U2) participants are asked to complete the IPAQ to assess physical activity. Next participants are placed on the examination table in a prone position for an ultrasound scan to measure the thickness of the M. erector spinae on the right side. The probe head is coated with coupling gel and applied perpendicular to the muscle on the right side without pressure to not compress the dermal surface. The images are saved, and the distance is measured later. Participants are then familiarised with the ILEX machine and positioned for individual adjustments. After a warmup for 120s with a low load and a short break, participants are asked to move dynamically into full flexion and full extension over the full ROM for three times. The test is repeated a second time. After a 2-minutes break, participants are asked to slowly move backwards to maximal tension and repeat the isometric force test after 2-minutes break. Next, the participant is seated in front of the sit-and-reach test box keeping the knees fully extended and the feet dorsiflexed against the foot-support. The participant is moving actively, slowly forward, bringing the body to the pain-free limit. The participant's hands move along the scale on the block until the movement is terminated because the participant can go no farther. The final position is held with an isometric contraction for 2 seconds, and the distance is read on the scale. After a 2-minutes break, the test is repeated. The rating scales for perceived effort, discomfort and thermal sensation are then presented for familiarization. Finally, the isometric back extension endurance is measured through the Biering-Sørrensen test. The participant is lying prone on an examination table with the upper border of the iliac crests in line with the edge of the table. The lower body is secured to the table by three straps around the pelvis, knees, and ankles. With the arms folded across the chest, the participant is asked to hold the upper body isometrically in a horizontal position. A stopwatch is used to measure the time the participant can keep the unsupported upper body in contact with a horizontal object. The examination takes about 1 hour.

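### Only participants are blinded, and nothing in the plan keeps the person who gives the diathermy or sham from running the effort-dependent force test and the hand-timed endurance test.

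*Combined protocol and SAP*

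**What the plan says.** Section 3.3 calls the preheating comparison a "single blinded randomized controlled trial". It explains the blinding from the participant's side only: "In order to be able to carry out a single-blind situation as far as possible, the test subjects are not told" that deep heat is the factor under study. Sham is delivered "with the Tecar device turned off and not sending radiofrequency before each exercise session". Under section 4.3 participants lie prone, "receiving a treatment with the diathermy device for 10 minutes from a trained examiner".

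The primary endpoint (section 3.2) is maximum voluntary isometric contraction of the back extensor, with peak torque registered by the machine. On test days, section 4.3 says that "participants are asked to slowly move backwards to maximal tension and repeat the isometric force test after 2-minutes break". For the Biering-Sørensen test, which section 3.2 includes to confirm the strength gain, section 4.3 says: "A stopwatch is used to measure the time the participant can keep the unsupported upper body in contact" with a horizontal object.

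Neither test description names the person running it. No section provides for blinded assessors, for keeping the allocation from testers, or for separating treating from testing staff. Section 5.1 contains no analysis directed at this source of bias.

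**The concern.** The second primary hypothesis in section 3.1 is that strength improves more with diathermy than with sham. A maximal voluntary contraction is only as high as the effort the participant gives, and that effort can respond to how the tester instructs and encourages. A tester who knows the arm may, without intending to, press harder in one arm. The endurance test is open to the same influence, and in addition someone has to decide by eye when contact is lost and stop the watch.

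If one informed person runs both tests, the primary result and the result meant to confirm it can move in the same direction for the same wrong reason. The analysis cannot detect or remove such a shift afterwards, because it looks exactly like a treatment effect.

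**Working it through.** **Who can know the arm, and who tests**

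| Step | Source | What is stated | Knows the arm? |
|---|---|---|---|
| Participant information | 3.3 | Heat is not mentioned | Intended not to |
| Diathermy or device-off sham | 3.3, 4.3 | Given by a trained examiner | Yes, necessarily |
| Effort rating after each session | 3.2 | "the examiner asks the participant" | Not stated |
| Isometric force test | 3.2, 4.3 | Tester not named | Not stated |
| Biering-Sørensen timing | 3.2, 4.3 | Timekeeper not named | Not stated |

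The plan therefore permits the treating examiner to run both tests, but does not say that this happens.

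**Where bias can enter**

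- Force: the reading is electronic (3.2) and saved automatically (8.2), so that route is closed. The effort route is open.
- Endurance: both the effort route and the stopwatch route are open.

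**The plan's own figure**

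Section 5.1 gives n = 10 for a within-between interaction with 2 groups, 3 measurements, effect size 0.46, alpha 0.05 and power 0.8. I take 0.46 as Cohen's f and assume correlation 0.5 between measurements and sphericity, none of which the plan states.

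- λ = f² × N × m / (1 − ρ) = 0.46² × 10 × 3 / 0.5 = 12.70, with 2 and 16 degrees of freedom. Power is 0.833.
- N = 8 gives 0.709, so N = 10 reproduces. At the 14 to be recruited, power is 0.952.

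The concern does not depend on this figure, and the fix does not change it.

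**Illustration of size**

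The documents give no size for tester-induced bias, so the shift b is an assumption. It is the between-arm difference in change caused by testing alone, in SD units of individual change, with no true treatment effect. An equal split of 14 gives 7 per arm.

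- Two-sided t-test on change, df = 2 × 7 − 2 = 12, critical value 2.179.
- Noncentrality δ = b × √(7/2) = 1.871 × b.
- False-positive rate = P(T > 2.179) + P(T < −2.179), with T noncentral t(12, δ).

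| Assumed shift b | δ | Either direction | Favouring diathermy only |
|---|---|---|---|
| 0 | 0 | 5.0% | 2.5% |
| 0.1 | 0.187 | 5.3% | 3.7% |
| 0.25 | 0.468 | 7.2% | 6.3% |
| 0.5 | 0.935 | 13.9% | 13.6% |

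The last column assumes that the shift favours diathermy.

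The t-test simplifies the planned interaction test. For the 2 × 3 interaction under compound symmetry, with the same shift at both follow-ups, λ = (14/3) × b² with 2 and 24 degrees of freedom. This gives 5.3%, 7.0% and 13.6% for the same three shifts, so the simplification does not drive the result.

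**The case against.** The strongest reply is that the plan already limits the risk. The machine registers peak torque, so a tester cannot alter the reading. The force instruction is partly standardised in section 3.2 (a slow, continuous extension over 2 to 3 seconds), and the test is repeated after a break. The endurance test has a physical contact criterion. Section 4.3 puts testing on separate days, and section 3.4 requires at least 48 hours after the last training session. Nothing in the documents shows differential encouragement, and the shifts used above have no source in them; at 0.1 SD the effect is negligible. All of this stands. It narrows the primary endpoint's exposure to the effort route but does not close that route, and it leaves the timing judgement in the endurance test open.

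Two stronger readings are tempting, and the documents do not support them.

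- A reader might infer that examiners who know the allocation do run the two tests. The test descriptions name nobody. The word examiner is used for giving diathermy, for the effort rating after training, and for consent questions and privacy, but not for the force or endurance test. The plan is silent on this.
- A reader might infer that the present team can certainly separate the roles without extra staff. Sections 4.2, 8.3 and 10 mention investigators, a laboratory team and examiners in the plural, but give neither numbers nor duties.

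A further fair point is that bringing in a different tester at follow-up only would add between-tester variation to each change score, which matters with about 7 per arm. The fix has to cover baseline as well.

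**Conclusion.** The concern holds as a gap in the design: participants alone are blinded, the person giving treatment knows the arm, and the plan neither names the testers nor stops that person from testing. This leaves the arm comparison open to bias on a voluntary-effort primary endpoint and on a hand-timed secondary endpoint meant to support it. Whether bias would occur, and how large it would be, is unknown. The range of 5.3% to 13.9% false positives rests on assumed shifts of 0.1 to 0.5 SD, 7 completers per arm and no true effect. It shows sensitivity and is not an estimate.

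The point should be corrected before testing starts, because prevention is the only remedy and most of it costs little. It does not affect the sample size, the choice of endpoints or the planned analysis.

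**What to change.** In section 4.3, under the examination days:

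1. Set one fixed instruction script for the force test and the Biering-Sørensen test at BL, F/U1 and F/U2. Wording and encouragement should be the same for every participant, and earlier results should not be displayed.
2. Where the existing team allows, have all three test visits of a participant run by the same examiner, who does not treat that participant and has no access to the allocation. Keeping one tester from baseline on avoids adding between-tester variation to the change scores.
3. Where this is not possible, keep the script and record on the CRF that the tester was unblinded.

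Section 3.3 should then state who is blinded and who is not.

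Cost: the script is about one page and needs no staff. Separating the roles means rostering 3 × 14 = 42 test visits, with less scheduling freedom. Tests are already planned on separate days from treatment, which makes this easier. Because team size is not stated, full separation may not always be possible without added staff, and none should be required; step 3 covers that case.

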3.4. Study intervention

We recruit a cohort of 14 healthy persons, both men and women, who have not trained their back extensors in isolation in the last 12 months. During a 6-week program consisting of a total of 12 sessions, the participants receive a diathermy treatment with the CE-certified device Tecar (T-Plus, Wintecare SA, Chiasso, Switzerland) and carry out a back extensor resistance training on the CE-certified ILEX machine Myosom (Heftec GmbH, Oberurnen, Switzerland).

Participants are randomly assigned to either the sham group, which receive a 10-minute treatment with the diathermy device turned off and not sending radiofrequency before each exercise session, or the intervention group, which undergo a 10-minute diathermy treatment to induce 448kHz capacitive monopolar radiofrequency and facilitate warming up of deep tissues. After all treatments participants are asked to rate their thermal sensation and comfort.

After the 10-minute diathermy treatment, the participants are seated in the ILEX machine in a semi-seated position with the feet placed on a footrest. The lumbar back is leaning against a round restraint that is free to rotate on its axis, the thoracal back against a squared restraint, hosting the load cells measuring torques produced by the left and right side separately. The machine incorporates a counterweighting procedure to counterbalance the effect of gravity acting on the upper body. Restraining belts are secured around the pelvis and around both shoulders. Over the anterior part of the upper thigh a restraint pad is positioned. All restraints

are tightened until a pressure but not pain occurs. These restraints prevent unwanted vertical movement of the pelvis or thighs.

Training will take place twice a week, beginning with a dynamic warm-up of the lumbar extensor for 120s, followed by three sets of resistance training lasting 120s, 120s, and 150s respectively, and concluding with a final set of dynamic recovery lasting 60s. 30-second recovery will be provided between every set. A low load will be used for the warm-up and recovery. The initial load is based on the maximum isometric force and subsequently increased until volitional fatigue. Repetitions will be executed by taking three seconds from complete flexion to complete extension, ensuring standardization at 20 repetitions per minute. A metronome with 40 beats per minute will provide audible feedback. The ILEX machine emits an audible signal upon completion of each phase of the repetition to guarantee a complete range of motion (ROM) is achieved. Subsequent to every training session, participants will be requested to provide their effort (RPE-E) and discomfort (RPE-D) values.

Baseline (BL) measurements are conducted before the initiation of training, and two follow-up measurements (F/U 1 and F/U 2) carried out after the sixth and twelfth session, with a minimum break of 48 hours after the last training session to ensure proper recovery and to prevent inaccuracies in muscle thickness measurement arising due to acute edema. At BL, participants need to give written informed consent and be familiarized with the ILEX machine and Category-Ratio-Scale (CR10) for the assessment of perceived effort and discomfort as well as a 9-point Likert scale for thermal sensation and 5-point scale for comfort. BL assessment include epidemiological data such as age, sex, height, and weight. Physical activity is assessed using the self-administered short German version of the International Physical Activity Questionnaire (IPAQ) with a "last 7 d recall" (IPAQ Research Committee, 2005) at BL, F/U1 and F/U2. At all three measurements (BL, F/U 1, F/U 2), the lumbar extensor musculature thickness (M. erector spinae), the maximum ROM, the maximum voluntary isometric contraction, the lower back flexibility, and the isometric back extension endurance are measured. Skin temperature is measured using an infrared thermal imaging (FLIR A615 series, Emitec Industrial, Rotkreuz, Switzerland) after the first and final diathermy treatment.

